Three main metrics will be measured during the pilot study: *Percentage of Correctly Transcribed Words Using ASR, Articulation Accuracy, and Mean Length of Utterance (MLU)*. These metrics will show whether there has been improvement in the participant’s functional language abilities, and oral motor coordination skills. They will be

analyzed by several trained staff members who will observe each recorded and monitored session.

Subject Selection

Recruiting: Subjects will be recruited by contacting (e.g. email or telephone) teachers and professionals (e.g. speech-language pathologists and behaviorists) who work with children with autism, aged 4 to 8. The research team will reach out to school administrators, teachers, and specialists through the iTherapy network of contacts to recruit eligible K-2 students diagnosed with ASD and their teacher or specialist. The VR-based VAST platform is designed for use with early elementary school-aged students (grades K-2). In order to conduct the intervention and gather data that would be useful for further development of the product, the research study must include early elementary school students.

In order to recruit enough children within the study's target population and to encourage retention, the study team will use online advertising via social media and other platforms (e.g. Craigslist) to reach participants. All participants will be given an Apple device (iPhone 6 for VR or refurbished iPad mini for 2D) for participating in the study and a free download of InnerVoice (valued at \$99.99), an iOS AI-powered communication app that uses video self-modeling, designed and sold by iTherapy.

Number of participants: 6

Inclusion/Exclusion criteria: All participants will be recruited via campaigns posted on social media and/or other platforms: parents/guardians will be provided consent forms and all information regarding inclusion/exclusion criteria.

Children **under the age of 18** will be recruited and all protections mandated by NIH policy afforded to them.

In order to protect participants and their families from COVID-19 exposure, participants will undergo Aim 3's procedures within their homes: the subjects' data will be collected using a HIPAA-compliant telehealth video-streaming platform. The goal of this

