procedure is to minimize any potential exposure to infection as a result of participating in this study. The study's team will follow CDC-recommended cleaning and disinfection guidelines to ship and retrieve the prototype VR headset (that is, the bone-conduction headphones along with the goggles sans the iPhones, which the participants can keep as part of participating in the study).

The proposed study will not discriminate based on gender, sexual orientation or race. Participants will be recruited from a pool of children at participating clinics and educational facilities independent of the above-mentioned aspects. There are no exclusion criteria based on gender, sexual orientation, or race.

Because data prior studies strongly support no significant differences of clinical or public health importance in intervention effect between subgroups, then sex/gender and/or race/ethnicity will not be recorded as subject selection criteria.

Children with a medically documented history of seizure disorder will be excluded from the study. According to Carnegie Mellon University Entertainment Technology Center (2019), individuals with a history of seizure disorder should avoid using virtual reality media.

Study procedures / research method

Due to health and safety concerns associated with the COVID-19 pandemic, the feasibility procedures will be conducted through a HIPAA-compliant telehealth platform. The subjects' caregivers or parents will help measure the impact of two pieces of technology: the 3D VR-integrated headset with bone-conduction and the 2D tablet-based application.

In order to prevent the spread of pathogens among large groups of subjects, the number of participants has been reduced from 30 to 10. Ten ASD students between the ages of 4 and 8 will be recruited to participate in a 14-sessions-long study that will utilize the integrated VAST application. The subjects will each receive a different piece of technology: one group of five will receive a 3D VR-integrated VAST prototype, while the other group of five will receive a 2D VAST version on a tablet. Sessions will be held twice a week with each lasting approximately 30 minutes (i.e. 30 minutes +/- 5 minutes).

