sensory and stimulus overload is common in children with ASD. Children on the spectrum sometimes experience inability to focus or distress when exposed to a surplus of stimuli. Avoiding this overload is not a matter of simplifying learning materials but rather managing the perceptual load children are exposed to.

Should any Adverse Events (AEs), Serious Adverse Events (SAEs) — injuries, seizures, or emotional distress — and Unanticipated Problems Involving Risks to Subjects or Others occur, a session will be ceased immediately and a report submitted to the IRB within 48 hours by the on-site researcher. If an SAE were to occur — such as an injury or seizure — staff will contact emergency medical services to ensure the subject's safety. Staff will receive training in communication and behavioral de-escalation strategies, whose aim is to reduce subjects' exposure to emotional distress. The PI and Co-investigator, both certified autism specialists, will be responsible for implementing the training.

All stimuli and engagement topics will be thoroughly vetted to reduce any discomfort on the part of the participant. Research staff will be advised to immediately cease engagement upon any visual sign of participant discomfort. Participants will only participate in the study as a supplement, and not a replacement, of prescribed or existing therapies.

Monitoring and reporting of Adverse Events/Serious Adverse Events

The research team will monitor subjects' exposure to adverse events/SAE throughout the study. For example, we will ensure that the methods of data collection do not invade the privacy of students, parents, teachers, or schools. We will monitor participation and responses to oversee and reduce potential feelings of frustration or embarrassment. Additionally, all children using the VR headsets will be required to sit so as to avoid

falling or suffering other injuries that might occur from standing or walking while wearing the headsets.

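### The seizure exclusion covers only a documented history, although its stated reason covers any history (minor safety wording change)

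*Combined protocol and SAP*

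**What the plan says.** The inclusion/exclusion text under Subject Selection contains one medical exclusion: "Children with a medically documented history of seizure disorder will be excluded from the study". It is justified at once by a cited source, according to which "individuals with a history of seizure disorder should avoid using virtual reality media".

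On how eligibility reaches families, the same section says that "parents/guardians will be provided consent forms and all information regarding inclusion/exclusion criteria". Recruitment runs through teachers and professionals and also through online advertising.

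On exposure, Study procedures / research method says that "one group of five will receive a 3D VR-integrated VAST prototype", while the other group uses a tablet. The exclusion applies to the whole study, not only to the VR group.

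Risk / Safety Information names a seizure as an example of a serious adverse event. It provides for stopping the session, calling emergency services and reporting to the IRB within 48 hours. IRB Review / Ethics / Informed Consent has a parent or guardian present throughout testing and able to stop it.

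**The concern.** The rule is narrower than the reason given for it. The reason covers everyone with a history of seizure disorder. The rule removes only those whose history is medically documented. A child who falls between the two is one whom the protocol's own safety premise would keep away from VR but whom its criterion admits.

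Because parents are given the criteria, a parent who knows of a seizure disorder but holds no record of it could honestly conclude that the exclusion does not apply. If that child were placed in the VR group, exposure could recur over up to 12 sessions (14 less the first and last, which are reserved for testing), at home and supervised by telehealth. What is at stake is the safety of an individual child aged 4 to 8. No estimate, test or sample size is involved.

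**Working it through.** The check is mainly a comparison of texts.

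1. **Rule against reason.** The rule, "Children with a medically documented history of seizure disorder will be excluded from the study", has two conditions: a history of seizure disorder, and medical documentation of it. The reason, "individuals with a history of seizure disorder should avoid using virtual reality media", has only the first. The children covered by the reason but not by the rule are those with a seizure disorder and no documentation.

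2. **Is the gap closed elsewhere?** In the text available for review there is no wider seizure criterion, no seizure question at entry, no record review and no medical clearance before VR use. The nearest statement is that "parents/guardians will be provided consent forms and all information regarding inclusion/exclusion criteria", which passes on the criterion as written. The consent pages were not available, so this step says nothing about what they contained.

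3. **Do the safety procedures close it?** Stopping the session, calling emergency services, reporting to the IRB and having a parent present all limit harm. They act once a child is already using the device and do not decide who receives it.

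4. **Rough size.** The plan has no figure to reproduce, and the documents give no rate of undocumented seizure disorder. As an illustration only, assume a rate p of 0.5% to 1% among otherwise eligible children. The number of participants is given both as 6 ("Number of participants: 6") and as 10 ("Ten ASD students between the ages of 4 and 8 will be recruited"), so take a VR group of n = 5 as stated, or n = 3 if six children are split evenly (an assumption). Expected affected children in the VR group = n × p, and the chance of at least one = 1 − (1 − p)^n.

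| VR group n | p (assumed) | Expected children | Chance of at least one |
|---|---|---|---|
| 3 | 0.5% | 0.015 | 1.5% |
| 3 | 1% | 0.03 | 3.0% |
| 5 | 0.5% | 0.025 | 2.5% |
| 5 | 1% | 0.05 | 4.9% |

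The expected count scales in proportion to p. These figures count children who might be given VR, not seizures. The documents give no risk of a seizure provoked by VR.

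**The case against.** The strongest reply is that a seizure disorder is itself a diagnosis, so the qualifier most naturally says how the diagnosis is verified. For the gap to matter, three things must coincide: the parent knows of a disorder, no record of it exists, and staff enrol the child despite the report. The purpose of the rule stands in the next sentence, so anyone applying it is told why it is there. This stands as a reason to rate the point low. It does not remove the mismatch, because the text neither calls the phrase a verification method nor describes a verification step.

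A second reply is that the consent form is an obvious place for a VR and seizure warning. That also stands. A reader might infer that the study had no seizure screening at all, but the documents do not support this: the claim holds only for the text that could be read.

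Third, some of the protocol describes conduct in the past tense, notably the Outcome Measures table. If enrolment is complete, rewording changes nothing for this study. Other sections use the future tense, so the documents do not settle the matter.

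**Conclusion.** The point holds as a wording mismatch. Read literally, the criterion admits a child whose parent reports an undocumented seizure disorder, and that child may be given VR. The documents do not show that such a child was or would be enrolled.

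The group is probably very small. On the assumed rates above it amounts to at most 0.05 expected child in the VR group. No statistical result depends on it.

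Two stronger readings should be resisted. By assuming a rate of several percent, a reader might infer an appreciable chance that a child at risk is exposed. The documents supply no rate, so such a figure would carry no evidential weight, and it would still count exposure rather than harm. A reader might also infer that children of unsure parents need clearance from a clinician. Nothing in the documents identifies a problem with unsure parents, and the added burden cannot be sized.

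This is a cheap improvement, at the lowest severity.

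**What to change.** Replace the criterion with wording such as: *Any child with a known history of seizure disorder, by parent/guardian report or medical record, is excluded.* Apply it before a device is assigned, and so before the steps taken "to ship and retrieve the prototype VR headset" begin. No further clearance procedure is proposed.

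The cost is one sentence and an occasional child who must be replaced. One replacement is 1/10 = 10% of the sample if ten are enrolled, or 1/6 = 17% if six are. Because the exclusion covers the whole study, it also removes children who would have used the 2D tablet. With equal groups, about two are excluded for each one kept off VR (10/5 = 6/3 = 2). On the same assumed rates, expected exclusions on parent report run from 6 × 0.5% = 0.03 to 10 × 1% = 0.10 children.

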Change in Mean Length of Utterance (MLU) – participants (aged 4 to 8 years) will be given a pre- and post-test 15-minute language sample. MLU was calculated for tests and gain from pre-test to post-test was compared. This measure is calculated based on a change in the number of morphemes per utterance during pre-test and post-test language samples. During a five-minute period, two licensed speech-language pathologists (SLP) will observe a parent interacting and talking with their child. Both will SLPs transcribe the subjects' speech and calculate a mean length of utterance (MLU) for each subject. MLU will be calculated by determining how many bound and free morphemes are included within every spoken utterance produced by a subject. The total number of morphemes produced within the 5-minute period will be divided by total number of utterances, which will then produce the MLU for each subject. This procedure will be used for determining MLU in both the pre- and post-testing procedures.

Parent Perceptions of Communication Changes Resulting from Study Participation – this measure examined parent observations and perceptions of changes in their children's motor-speech, behavioral, and social communication skills after having participated in the study.

Change in Type-Token Ratios – type-token ratio measures the total number of unique words in a given segment of language. The goal of using this metric is to examine any change in lexical diversity following either the tablet- or VR-based treatment.

Change in Response Rate to Treatment Stimuli – Response rate gain will be measured to determine whether there are any significant changes in how often children responded to pre- and post-testing stimuli after having received treatment between the iPad Pro and VR goggles groups.

Each session will be monitored and recorded. Two members of the trained staff will then observe these videos and analyze the rates of the aforementioned metrics.

Outcome Measures

Type	Name	Time Frame	Brief Description

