Primary	Change in Percentage of Correctly Transcribed Words Using Automatic Speech Recognition	Seven weeks--each subject participated in the study twice a week over a 7-week period for a total of 14 sessions. The first and last sessions (session #1 and session #14) were reserved for pre-test and post-test language sample collection and assessment.	15-minute pre- and post-testing was performed using speech recognition software and transcribed by a licensed speech pathologist. Differences pre- and post-intervention were compared across groups and within groups.
Primary	Change in Articulation Accuracy	Seven weeks--each subject participated in the study twice a week over a 7-week period for a total of 14 sessions. The first and last sessions	Change in % of correct phonemes in each attempted stimulus

		(session #1 and session #14) were reserved for pre-test and post-test language sample collection and assessment.	
Primary	Change in Mean Length of Utterance (MLU)	Seven weeks--each subject participated in the study twice a week over a 7-week period for a total of 14 sessions. The first and last sessions (session #1 and session #14) were reserved for pre-test and post-test language sample collection and assessment.	Participants (aged 4 to 8 years) were given a pre- and post-test 15-minute language sample. MLU was calculated for tests and gain from pre-test to post-test was compared.
Secondary	Parent Perceptions of Communication Changes Resulting from Study Participation	Seven weeks--each subject participated in the study twice a week over a 7-week period for a total of 14 sessions. The first and last sessions (session #1 and session #14) were reserved for pre-test and post-test language sample collection and assessment	Parent observations -- perceptions of changes in their children's motor-speech, behavioral, and social communication skills after having participated in the study

Secondary	Change in Type-Token Ratios	Seven weeks--each subject participated in the study twice a week over a 7-week period for a total of 14 sessions. The first and last sessions (session #1 and session #14) were reserved for pre-test and post-test language sample collection and assessment.	A type-token ratio measures the total number of unique words in a given segment of language.

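### The secondary type-token ratio is described as a count of unique words in a segment of no stated length, so a child who merely talks more can appear to change in lexical diversity

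*Combined protocol and SAP*

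**What the plan says.** Change in Type-Token Ratios is one of three secondary outcomes. Under Study procedures / research method, the plan says that the "type-token ratio measures the total number of unique words in a given segment of language", and continues: "The goal of using this metric is to examine any change in lexical diversity following either the tablet- or VR-based treatment". The Outcome Measures table repeats the description almost word for word: "A type-token ratio measures the total number of unique words in a given segment of language".

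The time-frame column of that table says that sessions 1 and 14 "were reserved for pre-test and post-test language sample collection and assessment". This ties the outcome to those two visits. It does not say which sample is used or how much of it is scored.

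On scoring, the procedures text says only: "Two members of the trained staff will then observe these videos and analyze the rates of the aforementioned metrics". No section gives a total-word denominator, a fixed number of words or utterances, or a length correction. The 15-minute figures in the plan belong to the speech-recognition and mean length of utterance (MLU) outcomes.

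**The concern.** The number of different words in a speech sample depends on how many words are spoken. A longer sample from the same vocabulary contains more unique words, and each further word is more likely to be a repeat. So the count rises with the amount of speech, and unique words divided by total words falls. The name of the outcome points to the ratio and the description points to the count. The two err in opposite directions, and staff have no rule for choosing between them.

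A change in the amount of speech is quite possible here. The Background presents the VR product as a way to raise engagement and practice in producing speech, and how often children respond to stimuli is itself a secondary outcome. A treatment that only makes children talk more would look like a gain in lexical diversity under the count and a loss under the ratio. A real gain in vocabulary could be hidden under the ratio.

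**Working it through.** The plan gives no type-token figure, so there is nothing to reproduce. It also gives no word counts, vocabulary sizes or between-child variation. Every input below is an assumption chosen to show direction and range.

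**1. Power law.** Let unique words grow as (total words)^b with b = 0.5, 0.6 or 0.7. If speech is multiplied by k and vocabulary is unchanged, the count is multiplied by k^b and the ratio by k^(b-1).

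| k | Count, b = 0.5 / 0.6 / 0.7 | Ratio, b = 0.5 / 0.6 / 0.7 |
|---|---|---|
| 1.25 | +11.8 / +14.3 / +16.9% | -10.6 / -8.5 / -6.5% |
| 1.5 | +22.5 / +27.5 / +32.8% | -18.4 / -15.0 / -11.5% |
| 2 | +41.4 / +51.6 / +62.5% | -29.3 / -24.2 / -18.8% |

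**2. Fixed vocabulary.** Take V words with Zipf probabilities p_i proportional to 1/i. The expected number of unique words in N spoken words is the sum over i of 1 - (1 - p_i)^N. With V = 220, 500 or 1000 and N = 60 or 180:

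| k | Count | Ratio |
|---|---|---|
| 1.25 | +14.7 to +19.9% | -8.3 to -4.1% |
| 1.5 | +27.6 to +38.9% | -14.9 to -7.4% |
| 2 | +49.5 to +74.5% | -25.2 to -12.7% |

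Both models together, for 50% more speech: count +22 to +39%, ratio -7 to -18%.

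One case in full (V = 220): going from 50 to 100 spoken words takes the count from 30.7 to 50.4 (50.4/30.7 = 1.64) and the ratio from 30.7/50 = 0.61 to 50.4/100 = 0.50, with no change in vocabulary.

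**3. A real gain hidden.** Let vocabulary double from 100 to 200 words. At 50 words spoken on both visits the ratio rises from 0.53 to 0.60. If the child also speaks 100 words instead of 50 at post-test, the ratio falls from 0.53 to 0.49.

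**4. Group comparison.** Trials were simulated with 3 or 5 children per group and no vocabulary change. The log SD between children was 0.4 for baseline words and 0.3 for the post/pre ratio of words. One group was made more talkative at post-test. The table gives the share of trials in which the sign of the mean difference goes each way.

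| Extra speech in one group | Count favours that group | Ratio favours the other group |
|---|---|---|
| 10% | about 63-68% | about 58-65% |
| 25% | about 78-85% | about 64-78% |
| 50% | about 91-98% | about 77-92% |

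The 10% and 25% rows use 1,000 trials with (V, N) = (500, 60) and (1000, 180). The 50% row covers runs of 4,000 and of 1,500 trials per setting, the larger with (220, 60), (500, 60), (500, 180) and (1000, 180). Without bias each share would be near 50%. When each child is scored on equal numbers of words at both visits, the more talkative group is favoured in about 49-52% of trials even at 50% extra speech.

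**The case against.** **The name settles it.** The outcome is called a ratio throughout, its goal is lexical diversity, and the table column is only a brief description. The missing division by total words may well be a slip. That is a fair reading, and the larger effects on the count apply only if scorers follow the description over the name. But dividing by total words does not remove the dependence on length. It reverses its direction.

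**The sample is implied.** The table row points to the language samples of sessions 1 and 14, and the only language sample with a stated length is the 15-minute one given for MLU. That inference is reasonable, but no section makes it for this outcome. Equal minutes would still not give equal words.

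**The consequence is limited.** This stands. The outcome is secondary, in a pilot of 6 or 10 children depending on the section. The Statistical Design and Power section names MLU, SIS and articulation rate for ANOVA and states no test for this outcome. The simulation shows the sign of a difference, not a significant result. The documents support no particular difference in talkativeness, and if both groups talk equally more there is no systematic bias between them. Within-group change is still biased, and change following either treatment is what the stated goal asks about.

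**A stronger reading on MLU.** A reader might infer that the primary MLU outcome has a contradictory sample length, because the text says "participants (aged 4 to 8 years) will be given a pre- and post-test 15-minute language sample" and then "During a five-minute period, two licensed speech-language pathologists (SLP) will observe a parent interacting and talking with their child". The documents do not support that. The five minutes can be an excerpt of the fifteen, and the plan adds: "This procedure will be used for determining MLU in both the pre- and post-testing procedures". One coherent procedure at both visits gives no ground for bias. Which five minutes are scored is missing detail and forms no part of this point.

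**Conclusion.** The point holds for the type-token ratio and should be fixed. Scored as described, or as an ordinary ratio without length control, the outcome moves with the amount of speech when vocabulary has not changed. The direction, up for the count and down for the ratio, follows from how repeated words accumulate and held in every setting tried. The size rests wholly on assumed word counts and vocabularies.

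A reader might infer that the comparison of VR with tablet is certain to be misleading. The documents do not support that: it requires the groups to differ in how much their speech increases, and the bias is modest if that difference is small. Nor does the point reach any primary outcome.

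**What to change.** In the procedures text and the Outcome Measures table alike:

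- Define the outcome as unique words divided by total words.
- Name the session 1 and session 14 language sample on which it is computed.
- For each child, compute it on the same number of words at both visits, namely the smaller of that child's two totals, with a stated rule for which words of the longer sample are kept.
- State, before scoring, a minimum number of words below which the outcome is not computed.
- Report total words per sample beside it, so that a change in talkativeness is seen as such.

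The cost is wording, plus the words dropped from the longer sample: 1 - 1/1.5 = one third if speech rises by 50%, and 1 - 1/2 = one half if it doubles. Changes are then free of each child's own change in amount of speech, but levels are not comparable between children. Children with very little speech may have no value.

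A single word count common to all children is optional only. The Background says that a quarter of people with ASD are minimally verbal or non-verbal, and no speech-level criterion for entry is stated, so one such child could cut every sample to a few words.

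No new visits or measurements are needed. Sessions are recorded and data are kept for ten years beyond the project, so existing recordings can be rescored in this way.
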